DATA COLLECTED	
At a minimum, the following subject data will be collected or reported:
 
Pre-Procedure
 
• Demographics
◦ Age◦ Gender◦ Race and ethnicity• Vital Signs
◦ Height◦ Weight◦ BMI (calculated)• Subject medical history inclusive but not limited to:
◦ Previous Cardiovascular Disease History◦ Serum Creatinine/eGFR calculation◦ Diabetic Status◦ Anemia• Anticipated treatment plan 
Procedure Data
 
• Overall procedure data:
◦ Total time of procedure (first administration of CM to last administration of CM)◦ Access location◦ Catheter size/type◦ DyeVert Plus Disposable Kit (i.e. Smart Syringe and DyeVert Plus Module) Lot number◦ DyeVert Display (CMW) Serial number◦ CM brand/type/concentration(s)◦ Treatment type◦ Treated lesion details◦ Total fluoroscopy time◦ Additional imaging (e.g. FFR, IVUS, etc)◦ Contrast Media Information from CMW Unit: Cumulative Volume, Contrast Saved, percent Contrast Saved, set Threshold Volume amount, and percent of Physician Specified Threshold◦ Method of determining Threshold◦ Evaluation of treatment plan details◦ DyeVert System "Off" details: Reason system was turned off◦ Adverse Events

	Procedure Follow Up/Study Exit 
• All standard of care Serum Creatinine/eGFR calculations collected prior to discharge• Reason for study exit
STUDY TIMELINE	All data will be collected through discharge.

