7 STATISTICAL METHODS AND DATA ANALYSIS

7.1 Analysis of Primary Effectiveness Objective

The primary endpoint of the study is the mean percentage of CM volume saved. Analysis will be based on a one sample t-test. The formal statistical test will be based on a one-sided t-test against a fixed null hypothesis. The null and alternative hypothesis to be tested is:

$$H_0: \mu_{diverted} \leq 30\%$$

$$H_a: \mu_{diverted} > 30\%$$

where $\mu_{diverted}$ is the mean percentage measured volume saved. Successful rejection of the null hypothesis will demonstrate that the percentage of volume saved is statistically greater than 30%.

To account for the variation in contrast savings by procedure type, a supplementary analysis will be performed using a model to adjust for procedure type (PCI vs diagnostic). An additional analysis adjusting for physician will also be employed if deemed appropriate based on number of physicians and number of cases per physician.

7.1.1 *Sample Size Considerations*

The mean total contrast volume saved is expected to be at least 35%. Based on a sample size of 100 subjects and a one-sided 0.025 alpha level, greater than 80% power will be provided for a standard deviation of 16. A larger mean or smaller standard deviation would provide additional power.

To account for the possibility of unavailable contrast savings data or incorrect usage of the device, a 15% attrition rate will be utilized. A total of 118 subjects will be enrolled to obtain approximately 100 evaluable subjects. The following instances indicate subjects deemed unevaluable for the primary analysis.

- The DyeVert Reservoir was inadvertently turned off due to user error for > 1 injection.
- The DyeVert Reservoir was turned OFF for >1 injection due to an adverse event, not related to the device.
- The CMW did not provide contrast accounting details at the end of a case due to device deficiency.
- A contrast accounting error due to user error occurs for > 1 injection as defined in the procedure case report form.
- The treating physician determines that a blue tooth disconnection occurred resulting in inaccurate contrast accounting.

7.2 *Subgroup Analyses*

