A subgroup analysis of the primary endpoint will be performed based on access approach (radial versus femoral), body mass index (BMI), physician user and procedure type. For BMI, subgroups will be defined those with $BMI < 30 \text{ kg/m}^2$ versus those $\geq 30 \text{ kg/m}^2$. A two-sample t test will be performed to compare the primary endpoint between groups at the nominal 0.05 alpha level. For grouping physicians in more than two groups, an ANOVA model will be used.

7.3 *Additional Statistical Considerations*

The primary analysis of endpoints will be based on the population of subjects with evaluable data for that endpoint. Cases deemed unevaluable in the primary analysis will be summarized in a listing and a second analysis will be performed inclusive of these cases. Sensitivity analyses for missing data may be performed if warranted. In the event normality assumptions of statistical models are not met, logarithmic transformations or non-parametric methods will be employed. All data will be summarized by descriptive statistics, using the mean, standard deviation, median, interquartile range, or percentages, numbers of patients with events, etc. and the associated 95% confidence intervals, as appropriate.

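### Does the second analysis in 7.3 need a rule for cases in which the display gave no contrast total?

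*Combined protocol and SAP*

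**What the plan says.** The endpoint is set in 7.1: "The primary endpoint of the study is the mean percentage of CM volume saved". It is tested one-sided against 30%, and the parameter is defined there as a mean of measured values. Section 7.3 sets the primary population: "The primary analysis of endpoints will be based on the population of subjects with evaluable data for that endpoint".

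Section 7.1.1 expects losses: "To account for the possibility of unavailable contrast savings data or incorrect usage of the device, a 15% attrition rate will be utilized". It then lists five kinds of unevaluable subject:

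- two in which the reservoir was off for more than one injection (user error, or an adverse event unrelated to the device);
- one with a user accounting error on more than one injection;
- one decided by the physician: "The treating physician determines that a blue tooth disconnection occurred resulting in inaccurate contrast accounting";
- one with no output: "The CMW did not provide contrast accounting details at the end of a case due to device deficiency".

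For all of these, 7.3 says: "Cases deemed unevaluable in the primary analysis will be summarized in a listing and a second analysis will be performed inclusive of these cases". Its next sentence reads: "Sensitivity analyses for missing data may be performed if warranted".

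The minimum data list in the synopsis names one source for the endpoint: "Contrast Media Information from CMW Unit: Cumulative Volume, Contrast Saved, percent Contrast Saved".

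**The concern.** The second analysis is described as taking in all unevaluable cases, yet one category has nothing to take in. Unless a value is assigned, those cases drop out a second time, and an analysis labelled inclusive is not fully so. They are also the cases that 7.1.1 attributes to a device deficiency, in a study whose purpose is to evaluate the device in standard use. The missing-data sentence is optional, names no method and is not tied to the second analysis. If such cases were numerous and had low savings, the second analysis could look reassuring without having tested the exclusions that matter most.

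**Working it through.** **Inputs from 7.1 and 7.1.1.** Null 30%, expected mean 35%, SD 16, one-sided alpha 0.025, 100 evaluable, 15% attrition, 118 enrolled.

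**The plan's own figures.** Noncentrality = (35 − 30)/16 × √100 = 3.125 on 99 degrees of freedom, which gives power of 87.2%, consistent with the stated figure of more than 80%. Enrolment: 100/0.85 = 117.6, so 118. Allowance for all five categories together: 0.15 × 118 = 17.7, about 18 subjects. This is a planning figure, not a cap.

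**Which categories lack a value.** The reservoir-off, user-error and Bluetooth cases can each have a recorded percentage, possibly an inaccurate one. Entering them as recorded is the plain reading of 7.3 and a coherent check on the exclusion rule. Only the category with no display output leaves nothing to enter.

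**If absent totals are left out.** Let k be the number absent and n = 118 − k. Assume recorded cases have mean 35 and SD 16.

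Lower bound = 35 − t(0.975, n−1) × 16/√n

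| k | n | Lower bound (%) |
|---|---|---|
| 0 | 118 | 32.08 |
| 7 | 111 | 31.99 |
| 18 | 100 | 31.83 |

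The bound barely moves, so it gives no sign of how many cases are missing. The listing and the N of the analysis do.

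**If absent totals are filled with a common value v (no spread).**

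- Mean = [35(118 − k) + kv]/118
- SS = (117 − k) × 256 + [(118 − k)k/118] × (35 − v)²
- Lower bound = mean − t(0.975, 117) × √(SS/117)/√118

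For k = 7 and v = 0: mean = 35 × 111/118 = 32.92; SS = 110 × 256 + (111 × 7/118) × 1225 = 36,226; SD = 17.60; bound = 29.72.

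| v assumed (%) | Last k with bound above 30% | First k with bound below 30% |
|---|---|---|
| 0 | 6 (30.05) | 7 (29.72) |
| 10 | 9 (30.04) | 10 (29.81) |
| 20 | 16 (30.10) | 17 (29.97) |
| 25 | 27 (30.04) | 28 (29.97) |

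At v = 30 and k = 18: mean = (100 × 35 + 18 × 30)/118 = 34.24, SD 14.83, t = (34.24 − 30)/(14.83/√118) = 3.10, one-sided p = 0.0012. Smaller k gives smaller p.

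**Dependence on the observed mean.** With v = 0, the bound first falls below 30% at k = 4 if the observed mean is 34% (29.77), and at k = 19 if it is 40% (29.77). The standard error is 16/√118 = 1.47 points, so a result one point from 35% would be ordinary. No fixed count would serve as a trigger.

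**Limits of this illustration.** The documents give neither k nor v. The mean of 35 and SD of 16 are planning figures for the evaluable subjects. The second analysis also takes in reservoir-off, Bluetooth and user-error cases, whose mean and spread are unknown. The tables show orders of magnitude and do not predict the second analysis.

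**The case for a change.** The best argument for a change is that the second analysis is the plan's only committed check on excluding about 15% of subjects, and it cannot reach the category caused by device deficiency. A few sentences written in advance would cost nothing in data. They could enter every recorded total as recorded, count the absent ones, and set those once to 0% over all enrolled subjects as a floor. If that bound stayed above 30%, the matter would be closed. If not, the saving among absent cases at which the bound crosses 30% would be reported. This would also prevent a choice made after the results are seen.

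Part of this stands. The text is silent on absent totals, and a report should state the N of the second analysis and how many cases had no total. But entering recorded values and counting absent ones only writes down how the plan would be read anyway.

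The 0% fill is a different matter. It treats a failure to display as a failure to divert. The synopsis lists the display and the disposable kit as separate components, and nothing says that failure of the first to report means less contrast was saved. Zero is the harshest of several possible values, and experienced statisticians would differ on using it. The small counts in the table depend on that choice.

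**Conclusion.** No change to the plan is needed. This is a gap in detail that analysts fill sensibly. A mean of measured percentages takes the cases that have a measurement, the rest appear in the listing, and the missing-data sentence in 7.3 is available if they are many. Followed as written, the plan produces no wrong result: the primary test and the sample size are unaffected, and the label of a secondary analysis is slightly broader than its content.

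The point would gain weight only if absent totals were numerous and there were evidence of low savings in them. At the planned mean, that means 7 cases at zero saving or 17 at 20%, set against an allowance of about 18 for all five categories. The listing would bring such a situation to light.

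The conclusion rests on two assumptions. One is that the display is the only source of the percentage, which is inferred from a list described as a minimum. The other is that the recorded cases behave roughly as planned. Sections 3 to 5 and the procedure case report form were not available for this review and may already contain a rule, which would strengthen the conclusion.
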